4.1.1 Statistical hypotheses

The dual primary objectives are to assess the efficacy of durvalumab monotherapy compared to placebo in terms of PFS per RECIST 1.1 as assessed by BICR and OS. The study will be considered positive (i.e. a success) if either of the below null hypotheses are rejected based on the primary analysis of PFS or OS in the FAS.

The statistical hypotheses for primary PFS:

- H0: No difference between durvalumab monotherapy and placebo
- H1: Difference between durvalumab monotherapy and placebo

The statistical hypotheses for primary OS are:

- H0: No difference between durvalumab monotherapy and placebo
- H1: Difference between durvalumab monotherapy and placebo

The following statistical hypotheses for the key secondary endpoints of PFS and OS comparing durvalumab in combination with tremelimumab versus placebo will be tested if the null hypothesis for both dual primary endpoints (PFS and OS, durvalumab monotherapy versus placebo) is rejected (see Section 4.2.1):

• H0: No difference between durvalumab in combination with tremelimumab and placebo

• H1: Difference between durvalumab in combination with tremelimumab and placebo

Analyses will be stratified by disease stage (I/II versus III) based on the TNM classification and receipt of PCI (yes versus no).

Statistical analyses of the durvalumab in combination with tremelimumab group will be performed in the combination analysis set to ensure no bias is introduced from an imbalance in the follow-up and recruitment period.

In general, for efficacy and PRO endpoints the last observed measurement prior to randomization will be considered the baseline measurement. However, if an evaluable assessment is only available after randomization but before the first dose of randomized treatment then this assessment will be used as baseline. For safety endpoints, the last observation before the first dose of study treatment will be considered the baseline measurement unless otherwise specified. For assessments on the day of first dose where time is not captured, a nominal pre-dose indicator, if available, will serve as sufficient evidence that the assessment occurred prior to first dose.

Assessments on the day of the first dose where neither time nor a nominal pre-dose indicator are captured will be considered prior to the first dose if such procedures are required by the protocol to be conducted before the first dose.

In all summaries change from baseline variables will be calculated as the post-treatment value minus the value at baseline. The % change from baseline will be calculated as (post-baseline value - baseline value) / baseline value x 100.

4.1.2 Visit window for safety and PRO assessments

Time windows will need defining for any presentations that summarize values by visit. The following conventions should also apply:

- The time windows should be exhaustive so that data recorded at any time point has the potential to be summarized. Inclusion within the time window should be based on the actual date of assessment and not the intended date of the visit. For laboratory assessments, if date of assessment is missing, visit date will be used.
- All unscheduled visit data should have the potential to be included in the summaries.
- The window for the visits following baseline will be constructed in such a way that the upper limit of the interval falls half way between the two visits (the lower limit of the first post-baseline visit will be Day 2). If an even number of days exists between two consecutive visits, then the upper limit will be taken as the midpoint value minus 1 day.

For example, the visit windows for vital signs data (with 4 weeks between scheduled assessments) are:

- Day 29, visit window 2-42
- Day 57, visit window 43 70
- Day 85, visit window 71 − 98
- Day 113, visit window 99 126

Note that visits up to 28 days after the last dosing date will be considered as being on treatment for the purposes of visit windowing and may be assigned to an ontreatment visit. Visits after this will be considered as follow-up and may be assigned accordingly.

- For summaries showing the maximum or minimum values, the maximum/minimum value recorded on treatment will be used (regardless of where it falls in an interval).
- Listings should display all values contributing to a time point for a patient.
- For non-EPRO visit based summaries:
 - If there is more than one value per patient within a time window then the closest value to the scheduled visit date should be used, or the earlier in the event the values are equidistant from the nominal visit date. If there are two values recorded on the same day and the parameter is CTCAE gradable then the record with the highest toxicity grade should be used. Alternatively, if there are two records recorded on the same day and the toxicity grade is the same (or is not calculated for the parameter) then the average of the two records should be used. The listings should highlight the value for that patient that went into the summary table, wherever feasible. Note: in summaries of extreme values all on-treatment values collected are used including those collected at unscheduled visits.
- For ePRO based visit summaries, if there are multiple records within the same analysis visit window, then the closest assessment to the target date should be used (by date, time and sequence). If there are multiple records on the same day prior to the target day, then the latest assessment will be used (by time and sequence). If there are multiple records on the same day after the target day, then the earliest assessment will be used.
- To prevent very large tables or plots being produced that contain many cells with meaningless data, for each treatment group visit data should only be summarized if the number of observations is greater than the minimum of 20 patients dosed for safety summaries and 20 patients randomized for PRO summaries.

- For summaries at a patient level, all values should be included, regardless of whether
 they appear in a corresponding visit-based summary, when deriving a patient level
 statistic such as a maximum.
- Baseline of safety data will be defined as the last non-missing measurement prior to the first dose of study treatment. For laboratory data, any assessments made on day 1 will be considered pre-dose. If there are two visits equally eligible to assess patient status at baseline (e.g. screening and baseline assessments both on the same date prior to first dose with no washout or other intervention in the screening period) with assessment time missing, the average can be taken as a baseline value. For non-numeric laboratory tests (i.e. some of the urinalysis parameters) where taking an average is not possible then the best value would be taken as baseline as this is the most conservative. In the scenario where there are two assessments on day 1, one with time recorded and the other without time recorded, the one with time recorded would be selected as baseline.

Where safety data are summarized over time, study day will be calculated in relation to date of first treatment. When PRO data are summarized over time, study day will be calculated in relation to date of randomization.

Missing safety data will generally not be imputed. However, safety assessment values of the form of "< x" (i.e. below the lower limit of quantification) or > x (i.e. above the upper limit of quantification) will be imputed as "x" in the calculation of summary statistics but displayed as "< x" or "> x" in the listings.

4.1.3 Handling of missing and incomplete dates

Patients with a partial date of birth (i.e. for those countries where year of birth only is given) will have an assumed date of birth of 1st Jan [given year]) for calculation of age at randomization.

During the creation of the reporting database, partial start dates including, but not limited to: AEs, medications and subsequent therapy, will be imputed as follows:

- If only day is missing: impute day as the first day of the month (unless month and year are the same as month and year of first dose of study treatment, in which case day should be imputed as date of first dose);
- If day and month are missing: impute day and month as the first day of the year (unless year is the same as year of first dose of study treatment, in which case day and month should be imputed as date of first dose);
- If the start date is missing, then the analysis start date will not be imputed.

Partial end dates will be imputed as follows:

- If only day is missing: impute day as the earlier of either the DCO or the last day of the month;
- If day and month are missing: impute day and month as the earlier of either the DCO or the last day of the year;
- If the end date is missing, then the analysis end date will not be imputed.

If either both the start and end date of an AE or medication are missing, or the start date of an AE or medication is missing, but the end date is complete or imputed and on or after the date of first dose, then the AE or medication is considered treatment emergent or concomitant.

Partial death dates will be imputed as follows:

- If only day is missing: impute day as the latest of the first day of the month or the last known alive date + 1;
- If day and month are missing: impute day and month as the latest of the first day of the year or the last known alive date + 1;
- If the year is missing, then the analysis date will not be imputed.

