3.2.9 Best objective response (BoR)

BoR is calculated based on the overall visit responses from each RECIST assessment. It is the best response a patient has had following randomization but prior to starting any subsequent anticancer therapy (excluding radiotherapy) and up to and including RECIST progression or the last assessment in the absence of RECIST progression and subsequent cancer therapy.

Categorization of BoR will be based on RECIST using the following response categories: CR, PR, SD, PD and NE.

For determination of a best response of SD, the earliest of the dates contributing towards a particular overall visit assessment will be used. SD should be recorded at least 8 weeks minus 1 week, i.e. at least 49 days (to allow for an early assessment within the assessment window), after randomization (i.e. study day 50). For CR/PR, the initial overall visit assessment which showed a response will use the latest of the dates contributing towards a particular overall visit assessment.

BoR will be determined programmatically based on RECIST from the overall visit response using all BICR data up until the first progression event, the start of subsequent cancer therapy or the last assessment in the absence of progression/subsequent cancer therapy. The denominator will be consistent with that used in the ORR analysis. In particular, patients with no evidence of disease will be excluded.

For patients whose PFS event is death, BoR will be calculated based upon all evaluable RECIST assessments prior to death.

For patients who die with no evaluable RECIST assessments, if the death occurs \leq 119 days (i.e. 2 x 8 weeks + 1 week to allow for a late assessment within the assessment window) after randomization, then BoR will be assigned to the progression (PD) category. For patients who die with no evaluable RECIST assessments, if the death occurs >119 days (i.e. 2 x 8 weeks + 1 week) after randomization then BoR will be assigned to the NE category.

A patient will be classified as a responder if the RECIST criteria for a CR or PR are satisfied at any time following randomization, prior to RECIST progression and prior to starting any subsequent cancer therapy.

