3.4 Safety

Safety and tolerability will be assessed in terms of adverse events (AEs) (including serious adverse events [SAEs]), deaths, laboratory data, vital signs, electrocardiograms (ECGs) and exposure. These will be collected for all patients.

'On treatment' will be defined as assessments between date of the first dose and 90 days following last dose of the study treatment or up to and including the date of initiation of the first subsequent anticancer therapy (excluding radiotherapy) (whichever occurs first).

The safety analysis set will be used for reporting of safety data.

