3.4.1 Adverse events (AEs)

AEs and SAEs will be collected throughout the study, from the date of informed consent until 90 days after the last dose of the study treatment. The Medical Dictionary for Regulatory Activities (MedDRA) (using the latest or current MedDRA version) will be used to code the AEs. AEs will be graded according to the National Cancer Institute Common Terminology Criteria for AEs (CTCAE Version 4.03). A treatment emergent adverse event (TEAE) is an AE with an onset date/time or a pre-existing AE worsening (taking the last grade prior to dosing as the reference) on or following the first dose of study treatment through to 90 days after the last dose of the study treatment or initiation of first subsequent therapy (whichever occurs first). All AEs will be listed however only TEAEs will be summarized. For each treatment group, in the unlikely event of the two components being administered separately then date of first dose/last dose will be considered as the earliest/latest dosing date of either component.

Adverse events that have missing causality (after data querying) will be assumed to be related to study drug ("durvalumab or placebo" or "tremelimumab or placebo"), with the exception of causality assessments that are not applicable for the patient, e.g. causal relation to durvalumab for patients in the placebo arm.

AEs of special interest (AESI) and AEs of potential interest (AEPI)

Some clinical concepts (including some selected individual preferred terms [PTs] and higher level terms [HLTs]) have been considered "AEs of special interest" (AESI) to the durvalumab program. AESIs represent pre-specified risks which are of importance to a clinical development program.

The AESIs reported in the AstraZeneca-sponsored durvalumab studies are defined as AEs with a likely inflammatory or immune-mediated pathophysiological basis resulting from the mechanism of action of durvalumab and requiring more frequent monitoring and/or interventions such as systemic corticosteroids, immunosuppressants, and/or endocrine therapy. Endocrine therapies include standard endocrine supplementation, as well as treatment of symptoms resulting from endocrine disorders (for example, therapies for hyperthyroidism include beta blockers [e.g. propranolol], calcium channel blockers [e.g. verapamil, diltiazem], methimazole, propylthiouracil, and sodium perchlorate).

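### SAP 4.1.3 can date a subsequent anti-cancer therapy before the last study dose, because partial start dates have no floor there

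*SAP*

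**What the plan says.** SAP 4.1.3 covers three kinds of record with one rule: "partial start dates including, but not limited to: AEs, medications and subsequent therapy, will be imputed as follows". If the day is missing, the first of the month is used. If day and month are missing, the instruction is to "impute day and month as the first day of the year". The only exception concerns the first dose: when the partial date shares its month (or year), the first-dose date is used. No bound refers to the last dose or to discontinuation.

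The same section treats partial death dates differently. They have a logical floor: "impute day as the latest of the first day of the month or the last known alive date + 1".

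The subsequent-therapy date is then used in several places:
- SAP 3.4 (on-treatment definition), 3.4.1 and 4.2.13.1 (AEs) and 4.2.13.2 (laboratory data) close their windows with it. The TEAE window, for example, runs "through to 90 days after the last dose of the study treatment or initiation of first subsequent therapy (whichever occurs first".
- SAP 3.2.9 counts a response only if it occurs "prior to RECIST progression and prior to starting any subsequent cancer therapy".
- SAP 3.2.1 uses it as the TFST event date, and the attrition-bias PFS analysis in 4.2.2 censors by it.

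SAP 3.2.1 and 4.2.21 describe subsequent therapy as following discontinuation of study treatment; 4.2.21 also admits therapy on the same day.

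**The concern.** For AEs, early imputation with a first-dose floor is the cautious choice, because it keeps an ambiguous event inside the treatment-emergent window. For subsequent therapy the same rule works the other way: an earlier date closes that window sooner. A therapy that by definition follows study treatment can be dated in the middle of it. AEs and laboratory values recorded while the patient was still being dosed would then leave the main tables, and a response on study treatment could be lost from best objective response.

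Only patients who go on to further therapy are exposed. If uptake of further therapy differs between arms, the undercount would differ too.

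**Working it through.** The plan gives no figure to reproduce, so the check is the logic of the rule followed by worked dates.

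**When a conflict arises.** Let F be the first dose, L the last dose and S the true therapy start, with F ≤ L ≤ S.
- *Day missing.* The imputed date is the first of S's month, or F if F is in that month. Since S is not before L, this can precede L only if S and L share a calendar month. The largest error is L on the 31st with therapy the same day: 31 − 1 = 30 days.
- *Day and month missing.* The imputed date is 1 January of S's year, or F if F is in that year. It precedes L whenever S and L share a calendar year, apart from trivial cases (L on 1 January, or L = F). If F is also in that year, the imputed date is study day 1.

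**Worked dates (assumed for illustration).** The last column applies max(imputed date, L).

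| Case | F | L | S | Missing | Imputed | Days before L | With floor |
|---|---|---|---|---|---|---|---|
| a | 10 Mar 2020 | 20 Oct 2020 | 29 Oct 2020 | day | 1 Oct 2020 | 19 | 20 Oct 2020 |
| b | 10 Mar 2020 | 20 Oct 2020 | 1 Dec 2020 | day, month | 10 Mar 2020 | 224 | 20 Oct 2020 |
| c | 10 Sep 2020 | 20 May 2021 | 1 Jul 2021 | day, month | 1 Jan 2021 | 139 | 20 May 2021 |
| d | 10 Mar 2020 | 20 Oct 2020 | 15 Nov 2020 | day | 1 Nov 2020 | none | 1 Nov 2020 |

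In case b the TEAE window shrinks to day 1, and no post-baseline response can satisfy SAP 3.2.9. In case d the therapy falls in a later month than the last dose, so there is no conflict and the floor changes nothing.

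**How often a partial date would conflict.** The rule was run for every last-dose date from 2021 to 2024, assuming a first dose 224 days (8 × 28) earlier and a fixed gap from last dose to therapy. The shares are conditional on the date being partial.

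| Gap (days) | Day missing: share before L | Largest error (days) | Day and month missing: share before L | Mean error (days) |
|---|---|---|---|---|
| 1 | 94% | 29 | 99.5% | 155 |
| 7 | 74% | 23 | 98% | 154 |
| 14 | 51% | 16 | 96% | 153 |
| 21 | 28% | 9 | 94% | 151 |
| 28 | 5% | 2 | 92% | 150 |
| 42 | 0% | – | 88% | 147 |
| 90 | 0% | – | 75% | 133 |

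The mean errors depend on the assumed 224-day treatment length; longer treatment would allow larger ones.

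**What the floor leaves unrepaired.** In case b the TEAE window should run to 1 December, which is 42 days after L. The current rule loses 224 + 42 = 266 days; with the floor, 42 days of post-dose follow-up are still lost, but nothing before L.

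**The case against.** The case for leaving the rule alone has real weight.

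- *Rarity.* Protocol Table 2 requires at least the start date and a description of each subsequent therapy. It schedules collection at visits nominally no more than 8 weeks apart, so a year-only record should be unusual. This stands, and the largest errors depend on such records.
- *No primary result is touched.* Primary PFS counts events whether or not another therapy was started, and OS does not use the date. TFST is supportive, the attrition analysis is a sensitivity analysis, no formal test of BoR is planned, and safety is descriptive. This stands.
- *AEs do not disappear.* SAP 3.4.1 lists every AE, so a reader who inferred that events vanish from the report would go too far; they leave the summaries that use the subsequent-therapy cut-off. Summaries ignoring that cut-off would show them. Protocol 9.4.2.1 commits to those summaries, but SAP 4.2.13.1 makes them optional, so this backstop is weaker than it looks.
- *The definitions would expose the error.* A therapy dated before discontinuation contradicts SAP 3.2.1 and 4.2.21, so a programmer might notice. But no rule says what to do then. One could keep the impossible date and another could discard the therapy as not subsequent.

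A reader might also infer that ORR loses on-treatment responses directly. SAP 3.2.3 does not support that. It excludes patients who stop treatment without progression, take new therapy and only then respond; a response during study treatment does not fit that sequence. The route for lost responses is the responder definition in SAP 3.2.9.

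**Conclusion.** The point holds and is minor. Followed literally, SAP 4.1.3 can produce a start date that the SAP's own definition of subsequent therapy excludes. With only the day missing, the error is at most about 30 days and requires therapy in the calendar month of the last dose. With day and month missing, therapy in the same calendar year is enough, and the error can be months.

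An error close to a full year might be inferred as typical. It would need a last dose in late December, a first dose no later than the start of that year, and a year-only record. The illustrative averages are about 133 to 155 days.

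The affected outputs are the on-treatment, TEAE and laboratory summaries, BoR, TFST and the attrition-bias PFS analysis. The number of patients is unknown and probably low. The worked sizes rest on assumed dates; the conditions for a conflict follow from the rule itself.

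**What to change.** Add one sentence to SAP 4.1.3: a partial start date of subsequent anti-cancer therapy is imputed as the later of the date from the current rule and the date of last dose of study treatment, and no later than any known therapy end date, death date or data cut-off. This follows the approach already used there for death dates and agrees with SAP 4.2.21.

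The cost is one SAP sentence and one line of code. The limitation should be stated: when therapy truly began some time after the last dose, part of the 90-day post-dose follow-up may still be cut from the main tables, but no data from before the last dose are lost.

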3.4.7 Concomitant medication

Any medications taken by the patient at any time between the date of the first dose (including the date of the first dose) of study treatment up to the date of last dose of study treatment + 90 days in the study will be considered as concomitant medication. Any medication that started prior to the first dose of the study treatment and ended after the first dose or is ongoing will be considered as both prior and concomitant medication.

Allowed and disallowed concomitant medications will be presented by ATC classification and generic term.

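### A partial AE start date in the month or year of first dose is set to the first-dose date without checking the end date, so an AE that ended before dosing can count as treatment-emergent

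*SAP*

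**What the plan says.** SAP 4.1.3 (Handling of missing and incomplete dates) states its scope as "partial start dates including, but not limited to: AEs, medications and subsequent therapy, will be imputed as follows". The default is the first day of the known month or year. The exception moves the start to the first dose when the month and year match it ("same as month and year of first dose of study treatment, in which case day should be imputed as date of first dose"), or when only the year is known and matches ("unless year is the same as year of first dose of study treatment, in which case day and month should be imputed as date").

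The end date enters only in a later sentence of the same section, for records with no start date at all. There, an AE or medication is treatment-emergent or concomitant if both dates are missing, or if "the start date of an AE or medication is missing, but the end date is complete or imputed and on or after" first dose. Partial death dates, also in 4.1.3, do carry a guard against an impossible value: "impute day as the latest of the first day of the month or the last known alive date + 1".

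Three other SAP sections use the result:

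- **3.4.1:** "A treatment emergent adverse event (TEAE) is an AE with an onset date/time or a pre-existing AE worsening" on or after first dose. The end date plays no part, and only treatment-emergent AEs are summarized.
- **4.2.13.1:** AEs that occur before the first dose go into the listings and, unless otherwise stated, stay out of the summary tables.
- **3.4.7:** concomitant medication is "Any medications taken by the patient at any time between the date of the first dose" and 90 days after the last dose, with the first-dose date included.

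**The concern.** Moving an uncertain start to the first dose is a sensible cautious default when the event might have been present on treatment. It is not sensible when the recorded end date shows that the event was over before dosing. The rule does not separate the two situations.

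AEs are collected from informed consent, and screening runs for 1 to 42 days before randomization and first dose (protocol Table 1 footnotes), so AEs that start and stop before dosing can be expected in the database. If one has a partial start, the written rule can put it into the treatment-emergent tables with an onset on the day of first dose. If it belongs to an AESI group, it can also enter the time-to-first-onset summary, and a negative value can enter the total-duration summary, which SAP 4.2.13.1 restricts to events that have an end date.

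**Working it through.** The plan gives no figure to reproduce, so the check is to apply the rules to dates and then ask how often the condition could arise.

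**1. The rule applied literally.** Assume a first dose on 20 March 2020, for illustration. Duration is taken as end − start + 1, an assumption because the SAP gives no formula for AE duration.

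| Recorded start | Recorded end | Imputed start | Treatment-emergent (3.4.1)? | Duration |
|---|---|---|---|---|
| March 2020, day unknown | 10 Mar 2020 | 20 Mar 2020 | Yes | 10 − 20 + 1 = −9 days |
| 2020, day and month unknown | 15 Feb 2020 | 20 Mar 2020 | Yes | −34 + 1 = −33 days |
| February 2020, day unknown | 10 Mar 2020 | 1 Feb 2020 | No | 39 days |
| 5 Mar 2020, complete | 10 Mar 2020 | none needed | No | 6 days |

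All four events ended before dosing. The first two are classed as treatment-emergent only because their start is partial and falls in the month or year of first dose.

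**2. Comparison inside 4.1.3.** Take an AE that ended on 10 March with no start date recorded. It fails the condition "the end date is complete or imputed and on or after the date of first dose", so it is not treatment-emergent under that sentence. If the site adds that the AE began in March, it becomes treatment-emergent. More information gives a worse classification.

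**3. Comparison with 4.2.13.1.** An AE with a recorded end before first dose occurred before treatment, so that section keeps it out of the summary tables. Sections 4.1.3 and 3.4.1 together put it in. The SAP does not say which prevails.

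**4. How often the calendar condition is met.** Inputs:

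- onset k = 1 to 42 days before first dose, equally likely (42 days from the protocol; uniformity assumed);
- first-dose dates on every day of four calendar years, 2018 to 2021 (assumed);
- exponential AE duration with mean m days (assumed; the documents give none).

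The probability that an AE starting k days before dosing has ended by first dose is w(k) = 1 − exp(−k/m). The share wanted is the sum of w(k) over onsets in the same month (or year) as first dose, divided by the sum of w(k) over all onsets.

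| Mean duration m | Same month | Same year |
|---|---|---|
| 3 days | 31.7% | 93.8% |
| 7 days | 27.6% | 93.4% |
| 14 days | 23.8% | 93.0% |
| 28 days | 20.8% | 92.7% |

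Without weighting by w(k), the shares are 35.1% and 94.1%. Those describe all onsets in the 42 days, including AEs still present at first dose. Conditioning on having ended moves onsets earlier and lowers the same-month share.

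The same-month column applies to records with only the day missing, the same-year column to records with only the year known. Neither says how many partial dates there are.

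**5. The proposed rule on the same records.** The first becomes 1 March 2020 (if consent was no later) and the second 1 January 2020 or, as an AE, the consent date if later. Neither is treatment-emergent. The other two do not change.

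**The case against.** **Medications.** A reader might infer that drugs stopped before dosing, such as steroids given with chemoradiotherapy, will flood the concomitant-medication tables. The documents do not support that. SAP 3.4.7 depends on the drug being taken on or after first dose, so a recorded earlier stop should keep it out whatever start is imputed. Protocol 6.4 asks for medication that the patient is receiving at enrollment or receives during the study, so a drug stopped months earlier need not be on the form at all. SAP 2.2 also provides for physician review of all medications before database lock, as part of identifying prohibited ones. What stands is that the imputed start falls after the stop.

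**AEs.** It can be said that 4.2.13.1 already states the right outcome. It states the intent, but a programmer who derives the treatment-emergent flag from 3.4.1 and the imputed date reaches the opposite result, and no cross-reference settles it.

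**Frequency.** Start and stop dates are required for each AE (protocol 8.3.4), and data queries are handled in the capture system. A screening AE with a known end and only the year of its start should be rare. This stands. It would be wrong to read the percentages as shares of screening AEs that are misclassified; they apply only to those with a partial start that ended before dosing.

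**Direction.** Over-inclusion is the cautious direction for safety. That is fair where the end date is unknown or on treatment, but not where it rules out exposure. A reader might also infer a biased comparison between arms. The same rule applies to every arm, and nothing in the documents suggests that partial dates differ by arm.

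**Conclusion.** The point holds for AEs as a gap in a stated rule. As written, 4.1.3 read with 3.4.1 turns an AE that demonstrably ended before dosing into a treatment-emergent AE with a start after its end, against the intent of 4.2.13.1 and against the SAP's own handling of wholly missing starts. For medications it produces an impossible date pair but need not change their classification.

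The size cannot be stated in absolute terms, because the number of partial dates is not given. Under the uniform-onset and exponential-duration assumptions, about 21–32% of the relevant AEs with the day missing, and about 93–94% of those with only the year known, would meet the condition. The consequence is some over-counting and some invalid durations in descriptive safety tables. No formal test is affected. It is a minor point, worth correcting because the correction is so cheap.

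**What to change.** Amend SAP 4.1.3 so that a partial start in the month or year of first dose is set to the first-dose date only if the end date is missing, ongoing, or on or after first dose. Otherwise impute the first day of the known month or year, for AEs no earlier than the informed consent date, and in every case no later than the recorded end date. The record then stays pre-treatment.

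The consent floor matters for year-only AEs: without it, 1 January could precede consent by months and replace one impossible date with another.

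The cost is one sentence in the SAP and one programming condition. Records with missing, ongoing or later end dates keep the cautious default, so nothing is lost where there is real uncertainty.
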